6.1.8. Data Adjustments/Handling/Conventions

All collected data will be presented in listings. Data not subject to analysis according to this plan will not appear in any tables or graphs but will be included only in the data listings.

Medical history and AEs (all types) will be coded using the current version of the Medical Dictionary for Regulatory Activities (MedDRA) and WHO Drug Dictionary (WHO-DD) Anatomical Therapeutic Chemical (ATC) classes and preferred terms.

For quantitative laboratory values reported as ‘<X’ or ‘≤X’, 1/2 times the lower limit of quantitation will be used for analysis. For values reported as ‘>X’ or ‘≥X’, 3/2 times the upper limit of quantitation will be used. Values above or below the limit of quantitation will not be flagged as abnormal unless they are outside the normal range for that laboratory test, as described in Section 9.2.

A treatment related AE is any AE with a reasonable possibility of being related to the study drug. Medical judgement will be used to determine relatedness, considering all relevant factors, including pattern of reaction, temporal relationship, relevant medical history, and confounding factors such as co-medication or concurrent diseases.

If partial dates occur for treatment emergent AEs, prior medications, or concomitant medications, the convention for replacing missing information for the purpose of statistical analysis is as follows.

Adverse Events

- If the event start date is completely missing, or if the subject was not treated, no imputation will be conducted.
- If the event start date is missing day and month, the treatment start date is not missing, and event start year is the same as the treatment start year, set the event start date to the treatment start date.
- If the event start date is missing day and month and the treatment start date is missing, the event start year is not the same as the treatment start year, or if there is information indicating that the event ended before the treatment start date (e.g., the event end date is before the treatment start date), then set the event start month and day to January 1st.
- If only the event start day is missing, the treatment start date is not missing, and the event start month and year are the same as the treatment start month and year, set the event start day to the treatment start day.
- If only the event start day is missing and the treatment start date is missing, or the event start month and year is not the same as the treatment start month and year, or if there is information to indicate that the event ended before the treatment start date, then set the event start day to the first day of the start month.
- End dates will not be imputed.

Prior and Concomitant Medications

Medication start and stop dates will not be imputed. Instead, available information will be used to assign the following categories to each medication: prior versus concomitant versus both. If a missing date part leads to uncertainty in how to assign categories, the medication will be considered concomitant.

For example, if the medication start year or end year is after the start of treatment, the medication will be considered concomitant even if the start month and/or day are missing. Likewise, if the medication start year occurs in the same year as the treatment start year, and the medication start

AD-ST-33.06 Effective date: 12-Nov-2020

month or end month is after the treatment start month, then the medication will be considered concomitant even if the medication start day or end day is missing.

7. Study Patients/Subjects and Demographics

7.1. Disposition of Patients/Subjects and Withdrawals

Disposition will include tabulations of the number and percentage of subjects randomized into each treatment group, completing the study, and withdrawing from the study, along with reasons for withdrawal overall and by treatment group. Additionally, the number and percentage of subjects assigned to each analysis population will be displayed. Tabulations will be for all subjects and will be displayed by the planned treatment.

Additionally, inclusion and exclusion criteria not met will be listed for screen failures.

7.2. Protocol Violations and Deviations

Protocol deviations will be tracked, recorded, and reviewed prior to database lock, following the Protocol Deviation Guidance Plan for this study. The deviation list will be stored in the Remarque system and transferred to the biostatistics team for analysis.

Protocol deviations will be classified as “Important” or “Non-Important”. An important deviation poses a possible safety issue to the participant, or it has a potential impact on the statistical analysis of the clinical data. A non-important deviation is identified as any protocol deviation that does not meet the criteria for an important deviation.

Examples of important deviations include but are not limited to:

- Violation of inclusion/exclusion criteria
- Randomization or dosing error
- Use of prohibited medications
- Assessment conducted by unqualified personnel
- Missing baseline efficacy or safety assessments
- Lack of adherence to study drug dosing
- Controlled substance inappropriate handling

Examples of non-important deviations include but are not limited to:

- Lack of data collection due to subject non-compliance
- Subjects who fail to make scheduled visits
- Extension of screening period to clarify diagnoses or verify laboratory values
- Incorrect storage of study drug
- Failure to follow up on subjects who drop out

Subjects with at least 1 deviation classified as “Important” will be excluded from the PP Population. The final decision regarding classification of deviations and inclusion and exclusion

of subjects from the analysis populations will be based on a final listing of protocol deviations. Subject inclusion/exclusion in analysis populations will be determined during a blinded review meeting before study data are unblinded. Clinical and Biostatistics team members will provide input to the decision and the final composition of the analysis populations will be approved by the Sponsor.

Protocol deviations will be summarized by treatment group and overall subjects for the All Subjects population. Data will also be presented in a by-subject listing.

7.3. Demographics and Other Baseline Characteristics

Summary statistics for demographic and other baseline characteristics will be presented overall and by treatment group. Demographic variables will include age, sex, race, ethnicity, height, weight, and body mass index (BMI). Baseline variables will include HAM-A total score, ADNLM total score, and IADQ total score. Demographic and baseline characteristic data will be summarized for the ITT and Safety populations.

Prior medications will be classified by ATC Class Level 2 and preferred term. The number and percentage of subjects taking each classification of medication will be summarized overall and by treatment group. The analysis will be conducted for the Safety population. Data will also be presented in a by-subject listing.

[figure not shown]
Medical and psychiatric history will be classified by system organ class (SOC) and preferred term. The number and percentage of subjects with each classification will be summarized overall and by treatment group. The analysis will be conducted for the Safety population. Data will also be presented in a by-subject listing.

Results from the Mini-International Neuropsychiatric Interview (MINI) and data on substance use will be presented in a by-subject listing.

7.4. Exposure and Compliance

Drug and placebo will be supplied in identical 10 mL amber glass vials with metered dose spray nozzle containing 8 mL of IP. Both drug and placebo nozzles will deliver 100 µL of IP. Each vial contains 40 doses of IP (8 mL/200 µL/dose = 40 doses). Subjects will be dispensed 2 vials of IP at Visit 2 (Baseline) and Visits 3 through 5. Vial weights will be recorded prior to dispensation. At Visits 3 through 6, the 3 vials dispensed at the previous visit will be returned. Weights of the returned vials will be recorded.

The difference in vial weight and doses missing will be computed for each subject and visit for which vials were returned (Visits 3 through 6). Details of these calculations are provided in Section 6.1.7.1. The calculation for doses missing does not differentiate between doses administered for priming purposes versus doses administered to the nasal cavity. It is assumed that priming practices are uniform across subjects and treatment groups. Differences in vial weight, differences in vial volume, and doses missing will be summarized by visit, overall and by treatment group for the Safety population.

8. Efficacy Analysis

8.1. Primary Efficacy Analysis

The primary endpoint will be tested for the following hypothesis:

H₁₀: Mean change in HAM-A total score from Visit 2 (Baseline) to Visit 6 does not differ between PH94B and placebo.

H₁₁: Mean change in HAM-A total score from Visit 2 (Baseline) to Visit 6 does differ between PH94B and placebo.

The estimand for the primary efficacy endpoint has the following components:

Table 4: Primary Efficacy Estimand

Attribute	Definition
Treatment	The treatment of interest is PH94B, 3.2 µg administered as an intranasal solution [REDACTED]. The active drug will be compared to a placebo control.
Population	The population of interest is adults with AjDA as defined by inclusion and exclusion criteria.
Variable of Interest	The variable of interest is change in subject reported severity of anxiety as measured by change from baseline in HAM-A total score using the SIGH-A, after 4 weeks of randomized treatment with study drug.
Intercurrent Events	Treatment discontinuation prior to the planned assessment time frame. Intercurrent events will be treated as described in Table 3.
Population Summary	The difference in change from baseline in mean HAM-A total score between PH94B-treated and placebo-treated subjects after 4 weeks of treatment.

Descriptive summaries of HAM-A total scores and change from baseline in HAM-A total scores will be provided for the primary endpoint by visit and by treatment group, based on the observed data.

An ANCOVA model with change from baseline to Visit 6 in HAM-A total scores as the outcome, treatment group as the factor, and baseline HAM-A as a covariate will be used to test the null hypothesis that there is no difference between PH94B- and placebo-treated subjects in mean change from baseline to Visit 6 in HAM-A total score. The analysis will be performed in the ITT population using SAS PROC MIXED. The following parameters will be presented: the change from baseline LS means and standard error (SE), 95% CI for the LS means, *p* value for testing if the LS mean is different than 0, LS mean difference between treatment groups (PH94B minus placebo) with SE, 95% CI for the LS mean difference, and *p* value for testing if the treatment LS means are equal.

If, for unanticipated reasons (intercurrent events), the fraction of subjects with missing change

AD-ST-33.06 Effective date: 12-Nov-2020

from baseline to Visit 6 HAM-A total scores is greater than 0.05, change from baseline to Visit 6 HAM-A total scores will be imputed using the fully conditional specification approach to multiple imputation as described in Section 6.1.4. If the fraction of missing change scores is ≤ 0.05 , missing change from baseline to Visit 6 HAM-A total scores will be imputed with treatment group mean change scores.

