7.4. Study Sites

It is projected that up to 2 centers will participate.

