9.5. Method of Assigning Subjects to Treatment Groups

In this parallel group, randomized study, subjects who meet study entry criteria will be randomly assigned in a 1:1 ratio to PH94B or placebo. The randomization schedule will be computer generated using a permuted block algorithm and will randomly allocate IP to randomization numbers. The randomization numbers will be assigned sequentially through a central interactive web response system (IWRS) as subjects are entered into the study. The randomization schedule will be stratified by site. Study center will not be a blocking factor in the randomization schedule.

The randomization schedule will be prepared by Premier Research before the start of the study. No one involved in the study performance will have access to the randomization schedule before official unblinding of treatment assignment. No subject will be randomized into this study more than once.

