13.1.4.2 Primary Analysis

An analysis of covariance model with treatment group as factor and baseline HAM-A as covariate will be used to test the null hypothesis that there is no difference between PH94B- and placebo-treated subjects in change from baseline to end of treatment in HAM-A scores. (SAS PROC MIXED, version 9.4).

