3.6. Method of Assigning Subjects to Treatment Groups

At Visit 2 (Baseline), subjects who meet study entry criteria will be randomly assigned to placebo or PH94B in a 1:1 ratio at each study site. The randomization schedule will be computer generated using a permuted block algorithm to randomly allocate IP to randomization numbers,

stratified by study site. A central interactive web response system (IWRS) will assign randomization numbers sequentially to subjects that are entered into the study. The randomization schedule will be prepared by Premier Research before the start of the study. No one involved in the study performance will have access to the randomization schedule before official unblinding of treatment assignment. No subject will be randomized into this study more than once.

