6.1.2. Adjustments for Covariates

For applicable efficacy models comparing change from baseline in efficacy measures of PH94B to placebo, the baseline value of the respective scale will be included as a covariate.

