treatment group. The regression model will include the following variables: baseline HAM-A total score, sex, age, LSAS total score, and analysis site. For each imputation process, a total of 25 complete datasets will be created. The random seeds to be used in the imputation process are 813616018 for the PH94B treatment group and 80521516 for the placebo treatment group.

The analysis method for the multiple imputation will match that described for the primary efficacy analysis in Section 8.1. Results from the multiply-imputed datasets will be combined using the standard Rubin's rules for multiple imputation (Little and Rubin, 1987) and will be done in SAS using PROC MIANALYZE.

Two sensitivity analyses will be performed to assess robustness of the multiple imputation results to changes in missing data assumptions. The sensitivity analyses include 1) a complete case analysis where only subjects with non-missing change from baseline in HAM-A total scores will be included, and 2) a control-case analysis, where missing change from baseline in HAM-A total scores will be imputed by the mean change from baseline for the placebo group. Sensitivity analyses are detailed in Section 8.1.1.

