6.1.6. Pooling of Sites

Analysis sites (pooled sites) will be created if any site has fewer than 6 randomized subjects. Site 004 will be one analysis site and all other sites will be combined into a second analysis site. The final determination of pooled sites will be made prior to database lock. Should the condition for multiple imputation be met, analysis site will be used in the multiple imputation model.

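### Randomisation is stratified by site, but the HAM-A ANCOVA has no site term: precision is lost if site predicts change, and the SE is overstated if allocation is also blocked within site

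*SAP*

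**What the plan says.** **Allocation.** SAP 3.6 has subjects "randomly assigned to placebo or PH94B in a 1:1 ratio at each study site", using permuted blocks stratified by site. Protocol 9.5 says "The randomization schedule will be stratified by site. Study center will not be a blocking factor in the randomization schedule".

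**Analysis.** Protocol 13.1.4.2 specifies "An analysis of covariance model with treatment group as factor and baseline HAM-A as covariate", and SAP 8.1 uses the same model: "treatment group as the factor, and baseline HAM-A as a covariate will be used to test the null hypothesis". SAP 6.1.2 says only that "the baseline value of the respective scale will be included as a covariate". The model is reused for the complete-case and control-case analyses (SAP 8.1.1), ADNM (8.2.3), IADQ (8.2.4) and HAM-A at Visits 3 to 5 (8.3).

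**Where site is used.** Site enters only the multiple imputation model, whose predictors are "baseline HAM-A total score, sex, age, LSAS total score, and analysis site". If any site randomises fewer than 6 subjects, SAP 6.1.6 pools: "Site 004 will be one analysis site and all other sites will be combined into a second analysis site". Protocol 7.4 says "It is projected that up to 2 centers will participate".

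The visible text gives no reason for leaving site out of the ANCOVA.

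**The concern.** A factor used to restrict randomisation would normally appear in the analysis model. When allocation is balanced within sites and sites differ in outcome, balancing makes the treatment difference less variable. A model without site cannot see this, so it counts the site difference as noise and reports too large a standard error. If allocation is not balanced within sites, the standard error is valid but the precision that site could supply is lost.

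Analysing change scores does not remove a rater difference between sites, because the model also conditions on baseline. Protocol 10 asks for the same rater throughout for each subject. That limits drift within a subject but not differences between sites.

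The trial has 40 subjects, and SAP 4 says its tests will inform the feasibility and design of Phase 2b and Phase 3. An avoidably wide interval would feed into that decision. The SAP also regards site as useful for predicting missing HAM-A change, then drops it when analysing that change.

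**Working it through.** **Inputs.** From the documents: N = 40, 1:1, two-sided 0.05, ANCOVA on treatment and baseline. Assumed: two sites, blocks of 4, within-site residual SD of 1, a site gap g in change given baseline, and a drug effect of 0.9 total residual SD. The synopsis gives no effect size, SD or power for N = 40, and protocol 13.2 is redacted, so the plan's own sample size cannot be reproduced. For orientation, 20 per arm gives 80% power at 0.886 SD in a two-sample comparison.

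**1. Rater shift.** Suppose a site's raters score s higher at both visits, and b is the slope of Visit 6 on baseline. The expected Visit 6 score is then a + s + b(baseline − s) = a + b·baseline + (1 − b)s. Given baseline, a site difference of (1 − b)s remains: 0.70s, 0.50s or 0.30s for b = 0.3, 0.5 or 0.7.

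**2. Blocked within site, 20/20.** Residual df are 37 without site and 36 with it.
- The site sum of squares is 40 × 0.5 × 0.5 × g² = 10g².
- About 37/38 of it is unexplained by baseline, so the mean square without site is about 1 + (10g² × 37/38)/37 = 1 + 10g²/38, against 1 with site.
- CI width ratio (without/with) ≈ √(1 + 10g²/38) × 2.026/2.028.
- The site share of residual variance is (g²/4)/(1 + g²/4).

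| Gap g | Share | Width ratio, formula | Width ratio, simulated | Type I error without site | Power without / with site |
|---|---|---|---|---|---|
| 0 | 0% | 0.999 | 0.999 | 5.0% | 78.0 / 77.9% |
| 0.30 | 2% | 1.011 | 1.011 | 4.8% | 78.3 / 78.8% |
| 0.46 | 5% | 1.026 | 1.026 | 4.4% | 78.5 / 80.0% |
| 0.67 | 10% | 1.056 | 1.056 | 3.9% | 79.1 / 82.1% |
| 1.00 | 20% | 1.123 | 1.123 | 2.9% | 80.1 / 86.2% |

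The simulation used 200,000 trials per cell. With site in the model, type I error is 4.9% to 5.0%. At g = 1.00 the reported SE is 0.360 against a true 0.322. The estimate without site is biased by at most 0.003 SD, which is simulation error.

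**3. Uneven sites, blocked.** For gaps 0.30, 0.46, 0.67 and 1.00, the CI without site is 0.6%, 1.8%, 4.1% and 9.1% wider at 30/10, and 0.2%, 0.9%, 2.2% and 5.2% wider at 35/5. Power forgone at 35/5 is 0.0, 0.5, 1.3 and 3.1 points.

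**4. Not blocked within site, 20/20.** Type I error without site is 5.0% throughout. For gaps 0, 0.30, 0.46, 0.67 and 1.00, the width ratios are 0.986, 0.997, 1.012, 1.041 and 1.105. Power without/with site is 78.0/76.8, 78.1/77.8, 78.2/79.0, 77.9/81.0 and 77.9/85.3%. The term starts to pay between gaps 0.30 and 0.46 (between 0.46 and 0.67 at 35/5).

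**5. Break-even.** With treatment balanced across sites, SE with site / SE without = √((1 − R²) × 37/36), where R² is the partial R² of site in the data. This equals 1 at R² = 1/37 = 0.027.

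A separate simulation with residual variance standardised agrees. At a 20% site share, blocked and 20/20, the model SE without site is 0.323 against a true 0.288, and the 5% test runs at 2.9%.

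**The case against.** The strongest reply is that nothing invalid has been shown. The model is prespecified, agrees with the protocol and belongs to a study the SAP calls exploratory. The only miscalibration is in the conservative direction. **This stands**, and it is why the point is an improvement rather than a fault that undermines the trial.

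No site gap is evidenced. Trained staff rate the HAM-A with a structured interview guide (protocol 10.3.1.1, SAP 6.1.7.2), and at b = 0.5 a gap of 0.67 would need a rater shift of 0.67/0.5 = 1.34 SD. **This stands in part**: the larger gaps are unlikely to come from raters alone. The guide reduces rater differences without excluding them, and case mix or placebo response can also differ between sites.

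The fix can cost power when allocation is not blocked within site and the gap is small. **This stands**, and the figures are in step 4.

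The pooled site factor may recover nothing. With assumed sites of 25/5/5/5 and effects 0, 0.5, −0.5 and 0, adding it made the CI 0.4% wider. **This is fair but limited**: those effects cancel within the pool. With a common gap of 0.67 across the pooled sites, the CI without site is about 5% wider.

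Finally, SAP 11 lists departures from the protocol. As the protocol model has no site term either, SAP 11 had nothing to record. **This stands.**

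**Conclusion.** The concern holds. There are three cases:

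- **Site predicts change and allocation was blocked within site.** The reported SE is too large, the test is conservative and precision is lost.
- **Site predicts change and allocation was not blocked within site.** The SE is valid and only precision is lost.
- **Site does not predict change given baseline.** Nothing is lost.

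The loss is negligible to small at gaps up to about 0.46 SD, or with very uneven sites. It reaches about 3 points of power at 0.67 and 6 at 1.00 with equal sites. These sizes rest on an assumed two-site layout, block size, site gap and drug effect, none of which the documents give. The direction does not depend on those assumptions. The change is worth making before unblinding because it is cheap; made afterwards it would be a post-hoc model choice.

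**What to change.** Before unblinding:

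1. Reconcile the two sentences in protocol 9.5 with each other, with SAP 3.6 and with the schedule actually generated. State whether blocks were formed within site.
2. Add site as a fixed factor to the ANCOVA in SAP 8.1 and list it in SAP 6.1.2. Use the randomisation site, or the pooled analysis site of SAP 6.1.6 if pooling is triggered. Reconcile the number of sites in protocol 7.4 with SAP 6.1.6, and say that the pooled factor may be coarser than the randomisation stratum.
3. Carry the term into SAP 8.1.1, 8.2.3, 8.2.4 and 8.3, and into the footnotes of Tables 14.2.1.1 to 14.2.1.3, 14.2.4.1, 14.2.5.1 and 14.2.6.1.
4. Record the departure from protocol 13.1.4.2 in SAP 11.
5. If the schedule was not blocked within site, describe the term as a choice made for precision, not as a match to the design.

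**Cost.** One model term, a few sentences and six footnotes. Two site levels use 1 df (37 to 36; critical t 2.026 to 2.028); more unpooled sites would use more. If site has no effect, the power cost is 0.1 point (20/20) to 0.3 point (35/5) under blocked allocation, and 1.2 points (20/20) otherwise.
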